9.7.2 Secondary analysis

For rare events, the rate per 100 patient-years will be provided considering the same approach than for the primary analysis. For relatively common events with recurrence, recurrent event methods might be considered. A yearly summary of event rate will also be provided for selected AEs and SAEs. See Section 9.3.2 for secondary endpoints definitions.

MedDRA PTs including bronchospasm, hypersensitivity, serum sickness, skin reaction, allergic oedema, anaphylactic reaction, anaphylactic shock, anaphylactoid reaction, anaphylactoid shock, angioedema, circumoral oedema, eyelid oedema, face oedema, lip oedema, lip swelling, oedema mouth, periorbital oedema, tongue oedema, laryngeal oedema, laryngospasm, laryngo-tracheal oedema, pruritus allergic, pruritus generalised, rash pruritic, type I hypersensitivity, urticaria as well as hypersensitivity (standardised MedDRA Queries SMQ) will be used for identification of hypersensitivity reactions.

An analysis will be performed for detection of complications of long term exposure to phenol in IP region. AE/SAE will be described by MedDRA classification, with a special focus on the events classified in the MedDRA high level group terms: Gastrointestinal tract irritation (SMQ), Abdominal pain (SMQ), Abdominal pain upper (SMQ), Abdominal pain lower (SMQ), "Mesotheliomas" and "Hepatobiliary neoplasms malignant and unspecified".

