7.2 RATIONALE

The extension of application for Insuman Implantable was obtained for "adult patients with type 1 diabetes mellitus that cannot be controlled with subcutaneous insulin (including pump) therapy, presenting with frequent, otherwise unexplained severe hyper- and/or hypoglycaemia." The pharmacovigilance activities proposed in the risk management plan (RMP) included routine pharmacovigilance activities to monitor the safety of Insuman and additional pharmacovigilance activities in the form of a non-interventional, prospective cohort study to further assess frequency of the risk related of the use of insuman in the implantable pump in routine clinical practice, especially long term safety.

This observational prospective study will provide important longitudinal data to add to the long term safety profile of intraperitoneal (IP) delivery of Insuman Implantable 400 IU/mL using the Medtronic Minimed implantable pump.

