9.2 SETTING

This registry will be multinational to ensure representativeness for this study be as exhaustive as possible due to limited number of patients treated with Insuman Implantable 400 IU/mL. The investigators and the patients will be strongly encouraged to participate.

The study population is a narrowly defined target population of patients with type 1 diabetes who meet the indication for use of CIPII because their diabetes is difficult to control. Specifically, Insuman Implantable is indicated for the treatment of adult patients with type 1 diabetes mellitus that cannot be controlled with subcutaneous insulin (including pump) therapy, presenting with frequent, otherwise unexplained severe hyper-and/or hypoglycaemia.

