9.3.1 Main Safety Criteria Definitions and Measures

9.3.1.1 Metabolic events

1. Severe hypoglycaemia defined as "An event requiring assistance of another person to actively administer carbohydrate, glucagons, or other resuscitative actions. These episodes may be associated with sufficient neuroglycopenia to induce seizure or coma. Plasma glucose measurements may not be available during such an event, but neurological recovery attributable to the restoration of plasma glucose to normal is considered sufficient evidence that the event was induced by a low plasma glucose concentration" (according to the EMA Guideline CPMP/EWP/1080/00 Rev.1, (5).

A severe hypoglycaemia may also fulfill criteria for SAE (hospitalization, coma, seizure).

- 2. Hyperglycaemia (caused by insulin under delivery due to pump jamming, pump dysfunction or catheter occlusion):
 - Any episode of hyperglycaemia with no apparent medical, dietary or insulin dosage reason will need investigation to identify the origin of the blood glucose (BG) increase. The origin of hyperglycaemia (pump jamming, pump dysfunction or catheter occlusion) will be recorded, as well as the corrective actions taken.
 - Can be associated with ketonemia > 0.5mmoL/L.

Non-Interventional Post Authorization Safety Study (PASS) Amended Protocol 220-Feb-2018HUBIN-C-06380 - insulin humanVersion number: 1

 Or with diabetic ketoacidosis (DKA). Diabetic ketoacidosis, defined as hyperglycaemia with symptoms such as polydipsia, polyphagia, polyuria, nausea, or vomiting; and presence of serum ketones, or moderate or large urinary ketones, will be confirmed with either arterial blood pH <7.25 or serum bicarbonate <15 meq/L; and treatment provided within a health-care facility. DKA is to be reported as an SAE.

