9.7.1 Primary analysis

Since the primary objective is to monitor the important identified risks (see Section 9.3.1 for primary endpoints definitions, the analysis will be descriptive and the multiplicity control will not be considered.

- For the important identified risks including severe hypoglycaemia, hyperglycaemia due to underdelivery of insulin, pump pocket infections, skin erosion, and abnormal wound healing, the time to first event will be depicted by the Kaplan-Meier methodology. Globally, the total number assessed will be given and the number and percentage of events/censored will be calculated. For each time point (six-month and each year time-points), the number of patients at risk, the number of events and the probability (Kaplan Meier estimates) of an event and its 95% confidence interval (CI) will be given.
- Graphically, the cumulative risk over the entire study using life table approach, as well as the instantaneous risk expressed as the hazard function over time, will be presented according to the time expressed in years and using a kernel smoothing method.

Moreover, a horizontal line will represent the incidence rate calculated, as number of patients with one or more events divided by the number of patients treated.

- For rare events, the incidence rate using time to event approach will be considered: number of patients with the event, total patients years for the event, and incidence rate per 100 patient-years with its 95% CI will be calculated.

For the analyses purposes, all AEs will be recorded in the study safety database and classified according to Medical Dictionary for Regulatory Activities (MedDRA® version 16.1 or later) by system organ class and preferred terms (PTs).

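### The primary analysis stops at the first event, although severe hypoglycaemia and under-delivery hyperglycaemia can recur and every episode is collected

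*Protocol*

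**What the plan says.** For the five important identified risks, Protocol section 9.7.1 states that "the time to first event will be depicted by the Kaplan-Meier methodology". It adds cumulative-risk and smoothed hazard plots, which in context follow the same first-event times. It also adds a horizontal reference line, labelled an incidence rate and defined as "number of patients with one or more events divided by the number of patients treated". For rare events only, it adds "number of patients with the event, total patients years for the event, and incidence rate per 100 patient-years with its 95% CI". The numerator there is again patients.

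Recurrence is mentioned in section 9.7.2: "For relatively common events with recurrence, recurrent event methods might be considered". The same paragraph promises a yearly event rate for selected AEs and SAEs, without naming them, and refers to section 9.3.2 for the endpoint definitions. The abstract has the recurrence sentence under Other analysis, with no link to an endpoint set.

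On data, section 9.3.1.1 treats hyperglycaemia episode by episode, with cause and corrective action recorded. Section 9.6.1 has AEs collected after every patient contact. Section 9.6.4.1 refers to dedicated e-CRF pages for severe hypoglycaemia and hyperglycaemia. Section 7.2 gives the purpose as assessing the frequency of the risks in routine use, with emphasis on long-term safety.

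**The concern.** A patient who has one episode leaves the risk set for that endpoint for the rest of the study. A patient with one severe hypoglycaemia and a patient with ten contribute the same single event. A second or third under-delivery episode in the same patient, perhaps years later, appears in none of the primary outputs.

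This has two consequences. First, frequency in the ordinary sense, episodes per unit of exposure, is not estimated in the primary analysis. If the metabolic events prove common, the rare-event rate does not apply to them, and the only figure called an incidence rate is a proportion with no person-time in it. Second, the shape over time can mislead. Patients at higher risk tend to have their first event early and drop out of the risk set, so the smoothed hazard can decline even if nobody's episode rate does. Section 9.9 recognises depletion of susceptibles among long-term users; a first-event hazard adds the same effect during follow-up. It matters more after the pump phase-out, because few new implants are expected and the cohort will consist largely of ageing devices.

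**Working it through.** The protocol states no event rate, precision or power figure for these endpoints, so there is nothing to reproduce. The check has two parts.

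**1. Which outputs count a second episode?**

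| Output | Section | Unit counted |
|---|---|---|
| Kaplan-Meier curve and estimates at 6 months and yearly | 9.7.1 | first event |
| Cumulative risk and smoothed hazard | 9.7.1 | first event, by context |
| Horizontal reference line | 9.7.1 | patients with an event / patients treated |
| Rate per 100 patient-years, rare events only | 9.7.1 | patients with an event |
| Recurrent-event methods | 9.7.2; abstract, Other analysis | episodes, but optional |
| Yearly event rate | 9.7.2; abstract, Other analysis | not defined; events not named |

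No primary output counts a repeat.

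**2. How large is the unused share?**

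Inputs:
- N = 260, from section 9.5.1.
- Follow-up T: section 9.2.1 caps it at ten years from entry of the first patient, and section 5 gives an estimated pump life of seven years. No mean is stated. T = 5 years is an assumption; 3 to 10 years was also run.
- Episode rate r on pump therapy: not in the protocol. Values of 0.02 to 2 per patient-year are assumptions.
- Between-patient dispersion k: an assumption, with k = 0 (Poisson), 1 or 2.

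Formulas, with m = r × T:
- P(at least one event) = 1 − exp(−m) for Poisson, or 1 − (1 + km)^(−1/k) for negative binomial.
- Unused share = 1 − P(at least one event)/m.

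Example with r = 0.2 and T = 5: m = 1, P = 1 − exp(−1) = 0.632, unused share = 1 − 0.632/1 = 0.368. In 260 patients that is 260 episodes and 164 first events.

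| r per patient-year (T = 5) | Episodes | First events (Poisson) | Unused, Poisson | Unused, k = 1 | Unused, k = 2 |
|---|---|---|---|---|---|
| 0.02 | 26 | 25 | 5% | 9% | 13% |
| 0.1 | 130 | 102 | 21% | 33% | 41% |
| 0.2 | 260 | 164 | 37% | 50% | 58% |
| 0.5 | 650 | 239 | 63% | 71% | 76% |
| 1.0 | 1300 | 258 | 80% | 83% | 86% |

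Over the whole grid the Poisson share runs from 3% (r = 0.02, T = 3) to 95% (r = 2, T = 10). More than half of episodes are unused only when the mean per patient exceeds 1.59 (Poisson), 1.00 (k = 1) or 0.72 (k = 2). At 5 years these means correspond to rates of 0.32, 0.20 and 0.14 per patient-year.

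**Shape of the hazard.** Under the negative binomial model each patient's rate is constant, yet the first-event hazard in the cohort at time t is r/(1 + k·r·t). With r = 0.2 and k = 1 it is 0.2 at entry and 0.2/(1 + 1 × 0.2 × 5) = 0.1 at five years. The plotted hazard halves while the true episode rate stays at 0.2.

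**The case against.** Time to first event is a legitimate descriptive measure of risk, and this study tests no hypothesis. Section 9.7 refers the complete overview of analyses to the amended SAP, which is not at hand and may contain an all-episode analysis. The yearly event rate in section 9.7.2 is a firm promise; both metabolic events are collected as AEs, so they may be among the selected ones. This stands to a degree: nothing is lost from the database, and the choice of variance method is ordinary SAP detail. But the protocol itself fixes a first-event primary analysis and leaves the alternative optional, and the yearly rate names neither endpoint.

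Three stronger readings are tempting and are not supported.

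- A reader might infer that the indication makes these endpoints recurrent, since it describes patients "presenting with frequent, otherwise unexplained severe hyper-and/or hypoglycaemia". That describes patients not controlled on subcutaneous insulin, not their event rate on the pump. The hyperglycaemia endpoint is also a different event, limited to device-caused under-delivery. Section 9.9 adds that long-term users may be at lower risk of some events. The protocol supports saying that the events can recur, not that they will recur often.
- A reader might infer that most episodes are thrown away. With no on-pump rate in the protocol, that depends entirely on the assumed rate; at 0.1 per patient-year over 5 years the Poisson figure is 21%.
- A reader might infer that recurrent-event methods are reserved for the section 9.3.2 endpoints. The cross-reference in 9.7.2 suggests it, but the abstract carries the same sentence without that link. The scope is unclear rather than restricted.

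**Conclusion.** The point holds as a mismatch between purpose and primary analysis. Section 9.7.1 contains no output that counts repeat episodes of severe hypoglycaemia or under-delivery hyperglycaemia, and the recurrent-event provision is optional with unclear scope. The primary analysis would therefore not show how often these events occur, and its hazard plot could suggest a declining risk where there is none.

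This structural finding rests on the text alone. Its size does not: the unused share is about 21%, 37% or 63% at assumed rates of 0.1, 0.2 or 0.5 per patient-year over an assumed 5 years under Poisson, higher with heterogeneity, and only a few per cent if the events are rare. The first-event analysis is not wrong and should stay. It is incomplete for two of the five primary endpoints, and the remedy is a worthwhile, inexpensive improvement.

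**What to change.** In section 9.7.1, for severe hypoglycaemia and under-delivery hyperglycaemia, commit to:
- total episodes per 100 patient-years, overall and by study year, over all follow-up time, with a 95% CI that allows for within-patient clustering (negative binomial or robust variance);
- a mean cumulative function plotted over time;
- time to first event, kept alongside as now.

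In section 9.7.2 and the abstract, replace the optional wording on recurrent-event methods with a commitment and state which endpoints it covers. Carry the same wording into the SAP.

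The cost is one extra table and one extra figure per endpoint. Episodes are already recorded, so no new data collection is needed.

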8.2 SECONDARY OBJECTIVES

The secondary objectives of the study are:

- To better characterize other important potential risks of Insuman Implantable 400 IU/mL: hypersensitivity reactions to Insuman Implantable 400 IU/mL, hypersensitivity reactions to pump material and focal hepatic steatosis,
- To gain more data about missing information: Safety in pregnant and lactating women and long term safety (including effect of long term exposure to phenol in IP region),
- To collect additional safety data with monitoring of adverse events.

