9 RESEARCH METHODS

9.1 STUDY DESIGN

This is a post approval, multinational, multicenter, observational, prospective cohort study for patients with type 1 diabetes who agree to participate. All patients on Insuman Implantable 400 IU/mL in the MIP will be encouraged to participate in this registry for the duration of the study, which is 10 years from inclusion of the first patient.

This registry will include a cohort of adults with type 1 diabetes some of whom are those already treated with CIPII and included in HUBIN_L_05335 as well as patients with type 1 diabetes placed on implantable pump more recently. Both types of patients in this cohort will be treated under normal conditions of use. This registry plans to collect safety information on the status of each patient with type 1 diabetes treated with Insuman Implantable 400 IU/mL in a Medtronic MiniMed Implantable pump. The information collected will include disease characteristics including comorbidities, concomitant medications and late diabetes complications, some important safety risks (identified and potential), and missing information described in the RMP.

The design of the study will mirror real life clinical practice and management of these patients. The visits will be done according to routine clinical practice for intra-peritoneal insulin (i.e. study entry, ad hoc, and refill visits). Sites will record data for study endpoint assessments at each visit every 40 to 45 days into the clinical record which is the source document and complete the electronic case report form (e-CRF) at least every six months.

In order to evaluate the real-life conditions of use of Insuman Implantable 400 IU/mL in a Medtronic MiniMed Implantable pump, the choice of a non-interventional design is more appropriate than an experimental design. Moreover the characteristics of interest may not be available or with insufficient accuracy in patient's electronic medical records; therefore a prospective mode of data collection for the purpose of the study objectives has been proposed.

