9.3.2.4 Other Adverse events

All other AEs will be reported, in particular, complications linked to phenol irritation will be reported as well as potential clastogenic effect of phenol and insulin mitogenic compound.

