9.6.1 Data collection schedule

The visits will be done according to routine clinical practice for CIPII, which includes routine visits approximately every 40 to 45 days and ad hoc visits for device interventions or BG control. The participating investigator will be asked to record all new patient data including patients new to the study but who may already be on CIPII at entry into the registry. After this initial data entry, sites will collect safety clinical data (AE/SAE) after each contact with the patient (routine scheduled visits every 40 to 45 days or at ad hoc visits). At three and six months after study entry, then every six months (corresponding approximately to the period for four refill visits), other patient data will be recorded in the e-CRF. AE/SAE will have expedited reporting. No post study follow up is required.

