9.6.2.3 Patient data

Data collection at the study entry (i.e. for new patients, the study entry visit should be performed as far as possible at the first clinical visit after pump implantation) will include the following:

- Patients training for pump use assessment,
- Date of signature of the ICF,
- Patient demography: date of birth, sex, weight, and height,
- Insulin history:
 - date of first insulin prescription (duration of type 1 diabetes),
 - indication for IP treatment,
 - initial date of IP treatment,
 - initial date of Insuman Implantable commercial treatment.
- Medical history:
 - Related to the pump use (including occurrence of DKA, hyperglycaemia and severe hypoglycaemia in the year prior to entry into registry or since pump implantation for new patients),
 - Comorbidities:
 - a) hypertension,
 - b) hyperlipidemia,
 - c) cardiovascular diseases.
 - History of diabetes complications (if any):
 - a) active proliferative retinopathy,
 - b) nephropathy,
 - c) neuropathy,
 - d) hypoglycaemic unawareness.
- Concomitant medications will include all medications at this study entry visit.
- Most recent serum glycosylated hemoglobin (HbA1c) value available (and laboratory normal range), with sampling date (No laboratory test is to be drawn in patients for the purpose of the study and timing of test not related to entry into study).
- Most recent urine microalbumin/creatinine ratio available and laboratory normal range, with sampling date (No laboratory test is to be drawn in patients for the purpose of this study).

After each contact with the patients (refill visits -approximately every 40 to 45 days - ad hoc visits or phone calls)

Non-Interventional Post Authorization Safety Study (PASS) Amended Protocol 2 20-Feb-HUBIN-C-06380 - insulin human Version

- Collections of AEs (in expedited manner see safety Section 11), including:
- Severe hypoglycaemia,
- Hyperglycaemia caused by insulin under-delivery (due to pump jamming, pump dysfunction or catheter occlusion),
- Pump pocket infection,
- Abnormal healing,
- Skin erosion,
- Hypersensitivity reaction to Insuman or pump material,
- Focal hepatic steatosis,
- Other AEs, including diabetic complications,
- Pregnancy/lactation.

All AEs will be followed until recovery or stabilization or until the end of the follow-up period, whichever comes first.

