9.7 DATA ANALYSIS

IQVIA will be accountable for the statistical analysis of the study data.

A complete overview of planned analyses and limitations due to sample size reduction will be available in the amended Statistical Analysis Plan (SAP).

Eligible patients will be those who have signed an Inform Consent Form (ICF) and have received at least one dose of Insuman Implantable 400 IU/mL. In this non-comparative cohort study, all data analyses will be purely descriptive and no statistical testing will be performed.

These descriptive analyses will be conducted on the entire study population and specific subpopulations of interest (eg, country).

Summary statistics (mean, standard deviation, median, interquartile range, minimum, and maximum values) will be presented for continuous variables and counts and, if relevant, percentages will be presented for categorical and binary variables.

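### The phenol analysis in 9.7.2 describes AE/SAE by MedDRA class only and does not commit to showing how events or patient-time fall by length of IP exposure

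*Protocol*

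**What the plan says.** Protocol 8.2 lists, among the missing information to be filled, "long term safety (including effect of long term exposure to phenol in IP region". Section 9.3.2.4 places the relevant events among the other adverse events: "complications linked to phenol irritation will be reported as well as potential clastogenic effect of phenol and insulin mitogenic compound".

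Section 9.7.2 gives the phenol question its own analysis, aimed at "detection of complications of long term exposure to phenol in IP region. AE/SAE will be described by MedDRA classification". The focus is on gastrointestinal irritation, abdominal pain, mesotheliomas and hepatobiliary neoplasms. The same section provides, in general terms, rates per 100 patient-years for rare events and a yearly summary for selected AEs and SAEs. It names no exposure-time variable, band or stratum.

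The cohort has mixed exposure at entry. Section 9.1 describes adults "some of whom are those already treated with CIPII and included in HUBIN_L_05335 as well as patients with type 1 diabetes" who were implanted more recently, and 9.6.1 expects "patients new to the study but who may already be on CIPII at entry into the registry". Section 9.6.2.3 collects the "initial date of IP treatment" and the "initial date of Insuman Implantable commercial treatment".

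On subgroups, 9.7 says: "These descriptive analyses will be conducted on the entire study population and specific subpopulations of interest (eg, country"). Section 9.9 offers separate analysis of long-term and new users as a possible remedy for depletion of susceptibles, and equates long-term users with patients from the clinical trials. The ENCePP checklist marks duration-dependent response (5.5) and stratified analyses (10.4) as not applicable.

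**The concern.** The question is about long exposure, and the stated method has no exposure axis. In a cohort where everyone started IP insulin at entry, study year would serve as one. Here an event in the first study year may follow a few months or many years of IP insulin, and a pooled or yearly figure treats the two alike.

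What is at stake is how a quiet result would be read. No mesotheliomas among patients observed mainly in their first years of IP treatment says little about long exposure. The same result among patients mostly beyond ten years says more. The planned summary would look the same in both cases.

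**Working it through.** The protocol gives no precision figure for this analysis, so there is nothing to reproduce. The check has three parts.

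**1. What is fixed.** Aim (9.7.2): complications of long exposure. Method (9.7.2): description by MedDRA class. Time scale of any rate: patient-years or yearly. Subgroup named (9.7): country, as an example. Remedy for mixed exposure (9.9): worded as a possibility, and tied to trial participation although 9.6.1 expects other patients already on CIPII. No exposure-time commitment appears in 9.7 to 9.7.3.

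**2. Study time against exposure time.**
- Study time: first patient April 2016, last patient out Q1 2026 (sections 5 and 6), so at most 10.0 years.
- IP treatment, counted only from the 1998 French authorisation of the earlier IP insulin (7.1): 0 to about 17–18 years at the first entries.
- Commercial Insuman Implantable, from September 2013 at the earliest: at most 2.6 years at first entry and 12.6 years by the end.

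On the IP clock, the possible spread at entry is wider than the whole follow-up. On the commercial Insuman Implantable clock it is not.

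**3. Illustration on assumed inputs.** From the protocol: 260 patients. Assumed: every patient followed for F = 5 years; a share n newly implanted; the rest with prior IP exposure uniform on 0 to M years. Two corners are used:
- A: n = 0.36, M = 9
- B: n = 0, M = 18

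The 0.36 takes the old ceiling of 50 new patients a year (9.9) for the 1.89 years from April 2016 to amendment 2: 50 × 1.89 ≈ 94, and 94/260 = 36%. This assumes the ceiling was reached and meant new implants.

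Share of patient-time at or beyond b years = mean overlap of [prior, prior + F] with [b, ∞), divided by F. New implants contribute nothing at b = 5 or 10 when F = 5.

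- b = 10, A: 0.64 × [(4²/2)/9]/5 = 0.114
- b = 10, B: [(12.5 + 40)/18]/5 = 0.583
- b = 5, A: 0.64 × [(12.5 + 20)/9]/5 = 0.462
- b = 5, B: [(12.5 + 65)/18]/5 = 0.861

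Exact 95% upper limit with zero events = 100 × [χ²(0.975; 2 df)/2]/patient-years = 368.9/patient-years.

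| Time since IP start | Patient-years (A to B) | Upper limit per 100 patient-years (A to B) |
|---|---|---|
| All, pooled | 1300 | 0.28 |
| ≥5 years | 601 to 1119 | 0.61 to 0.33 |
| ≥10 years | 148 to 758 | 2.49 to 0.49 |

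The limit at ≥10 years is therefore about 1.7 to 9 times the pooled one.

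A pooled rate can also hide a gradient. Take assumed true rates of 0.5 at short and 1.5 at long exposure per 100 patient-years. The pooled rate is then 0.75, 1.00 or 1.25 when 25%, 50% or 75% of patient-time is long. Each could equally be a flat rate.

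**The case against.** **The SAP may cover it.** Section 9.7 leaves the complete overview of analyses to the amended SAP, and table strata for a secondary descriptive summary are ordinary SAP detail. This stands as a caveat and keeps the point small. It does not remove it, because 9.7.2 states a method for this named question and leaves out the dimension that the question turns on. The two checklist entries give no sign that an exposure breakdown is intended, though the one on duration-response also fits a plan that claims no such estimate.

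**Section 9.9 already helps.** Its separate analysis mentions other AEs, so it could reach phenol events. That is right, but the protocol does not commit to it, and a long-standing CIPII user who was in no trial has no clear place in it.

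**The dates are there.** A reader might infer that the study cannot show whether events follow long exposure. The documents do not support that. IP start is recorded per patient, prior exposure can be summarised at baseline, and time since IP start can be derived for any case. What is missing is a commitment to tabulate it.

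**The 18 years are not shown to be phenol years.** This stands too. The protocol does not give the phenol content of earlier IP insulin. On commercial Insuman Implantable time alone, and leaving aside trial exposure of unstated length, study time is a fair proxy.

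**Conclusion.** The point holds as a modest improvement to the protocol. As written, 9.7.2 will not show how much of the observed patient-time or events lies at long IP exposure, and 9.9 does not firmly supply that.

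The numerical limits depend on assumed exposure mixes and a fixed five-year follow-up. They show that the pooled limit can differ materially from the long-exposure one, and they do not estimate by how much in this cohort. Corner A is an extreme: 9.9 says the recruitment target behind it will not be met, and the abstract expects few or no further new implants.

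A reader might also infer that the protocol promised a duration-response estimate and dropped it. It did not. The objective is to gain data, the analysis is for detection, and the study is declared purely descriptive.

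**What to change.** Add to 9.7.2: for the phenol focus events, the number of events, patient-years and rate per 100 patient-years with 95% CI will be tabulated by time since the initial date of IP treatment (for example <5, 5–<10 and ≥10 years), counting only follow-up after study entry. Each mesothelioma or hepatobiliary neoplasm will be listed with its time since first IP treatment and since first commercial Insuman Implantable.

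In 9.9, make the separate analysis of long-term and new users firm for these events, and define the groups by date of first IP treatment instead of trial participation.

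State the limits beside the table: sparse bands with wide intervals, survivor selection among long-exposed patients, confounding by age, and time since IP start as a proxy only, since the phenol content of earlier IP insulin is not given. The table would neither prove nor exclude a phenol effect.

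The cost is a few sentences, one table and a short listing, from dates already collected. No visit, test or change in sample size follows. A second table by Insuman Implantable time is not required; it would need trial exposure dates that the protocol does not list.
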